10.4	Protocol Amendment History	60
11	REFERENCES	61

STATEMENT OF COMPLIANCE

(1) The trial will be carried out in accordance with International Council on Harmonisation Good Clinical Practice (ICH GCP) and the following:

- United States (US) Code of Federal Regulations (CFR) applicable to clinical studies (45 CFR Part 46, 21 CFR Part 50, 21 CFR Part 56, 21 CFR Part 312, and/or 21 CFR Part 812).

The protocol, informed consent form(s), recruitment materials, and all participant materials will be submitted to the IRB for review and approval. Approval of both the protocol and the consent form(s) must be obtained before any participant is consented. Any amendment to the protocol will require review and approval by the IRB before the changes are implemented to the study. All changes to the consent form(s) will be IRB approved; a determination will be made regarding whether a new consent needs to be obtained from participants who provided consent, using a previously approved consent form.

1 PROTOCOL SUMMARY

1.1 SYNOPSIS

Title:	Intraoperative video laryngoscopy as adjunct for nerve monitoring
Grant Number:	N/A
Study Description:	
The purpose of this study is to describe the impact of adding intraoperative video laryngoscopy (IOVL) to intra-operative laryngeal nerve monitoring (IOLNM) during neck procedures when IOLNM is routinely used, including thyroidectomy and re-operative parathyroidectomy. Specifically, we seek to assess how frequently the use of IOVL provided confirmatory or additional information that may affect surgeon decision-making when IOLNM alone is ambiguous, or when there is equipment malfunction or failure. The IOVL is a disposable, otherwise standard fiberoptic laryngoscope (Larynxview, Neurovision Medical, Ventura CA) that is inserted alongside the endotracheal tube following intubation for surgical procedures. It allows assessment of vocal cord movement in response to nerve stimulation. Currently, the use of IOLNM is based on audio cues, and visual assessment of external laryngeal muscle movement during surgery in response to stimulation, but no direct assessment of vocal cord movement is routinely possible. This information can be ambiguous and subject to judgement of the surgeon. The addition of IOVL provides direct assessment to vocal cord movement in response to stimulus, and may be useful in light of ambiguous IOLNM data, or limited visualization of external laryngeal muscles.

Objectives* :	
This is a descriptive study in which we seek to assess the degree to which intraoperative video laryngoscopy used in conjunction with routine intraoperative nerve monitoring provides additional data on nerve integrity and vocal cord function for patients undergoing neck procedures that place the recurrent and superior laryngeal nerves at risk for injury or postoperative dysfunction. Specifically, we are interested in how frequently the information gained from video laryngoscopy may provide data on the vocal cord function in situations of ambiguous data from the nerve monitor, or in cases of equipment malfunction or failure of the nerve monitor. We would also like to assess the frequency of discordance in evaluation of intraoperative nerve monitoring, which is an indirect measure of vocal cord function via nerve integrity, with direct evaluation of vocal cord function via video laryngoscopy

Endpoints* :	
This is a descriptive study. There are no specific patient outcome endpoints. We will be primarily assessing the frequency with which the IOVL provides additional data to IOLNM which may be used to make further surgical decision making.

Study Population:	
125 patients over the age of 18 with a medical indication for partial or total thyroidectomy, re-operative parathyroidectomy, or neck dissection will be enrolled at Mount Sinai Hospital, Mount Sinai Beth Israel, Mount Sinai Morningside, and Mount Sinai West.

Phase* or Stage:	
Enrolling

[figure not shown]

Description of Sites/Facilities Enrolling Participants:	The Mount Sinai Hospital, Mount Sinai Beth Israel, Mount Sinai Morningside, Mount Sinai West
Description of Study Intervention/Experimental Manipulation:	Intraoperative video laryngoscopy will be used in conjunction with routine intraoperative nerve monitoring. We seek to asses the degree to which this will provide additional data on nerve integrity and vocal cord function for patients undergoing neck procedures that place the recurrent and superior laryngeal nerves at risk for injury or postoperative dysfunction.
Study Duration* :	We expect the study to take approximately 3 years.
Participant Duration:	3 months

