IOLNM is an indirect measure of vocal cord function. It provides information on nerve integrity via electromyography (EMG). The feedback the surgeon receives from the system is based on the amount of current necessary to stimulate vocal cord movement, with higher currents indicating worse signal transduction through the nerve, and a loss of signal indicating a severely injured or divided nerve. Surgeons are extrapolating vocal cord function based on auditory cues which indicate nerve integrity, as well as graphical information of the amplitude of the signal (known as the NPI or nerve power index), but do not routinely visualize vocal cord function in real time when making decisions during the procedure. In our experience, the current system has some limitations. The nerve power index (NPI) is a value displayed by the IOLNM system as an expression of nerve function, with higher numbers indicating better nerve conduction. The quality of conduction is audibly expressed by a two-tone system, with a higher-pitched tone occurring with an NPI >100, and a lower-pitched tone occurring with an NPI <100. Often the actual NPI is very close to 100, either higher or lower, and interpretation of nerve integrity in this range is ambiguous. Direct interpretation of vocal cord function could be of greater use to the surgeon at these times. We have also experienced system failures, either due to a break in the small wires of the electrode leads, or computer hardware or software malfunction, any of which can lead to the inability to use the IOLNM. In our experience, some form of failure or malfunction of the IOLNM system occurs in 10-15% of operative cases.

>100, and a lower-pitched tone occurring with an NPI <100. Often the actual NPI is very close to 100, either higher or lower, and interpretation of nerve integrity in this range is ambiguous. Direct interpretation of vocal cord function could be of greater use to the surgeon at these times. We have also experienced system failures, either due to a break in the small wires of the electrode leads, or computer hardware or software malfunction, any of which can lead to the inability to use the IOLNM. In our experience, some form of failure or malfunction of the IOLNM system occurs in 10-15% of operative cases.

Visualization of vocal cord function through an independent system offers another means to assess recurrent laryngeal nerve integrity in these situations.

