4 STUDY DESIGN

4.1 OVERALL DESIGN

This will be a prospective cohort study without randomization. Patients enrolled will undergo the planned procedure according to our routines of care. IOLNM will be performed per our routine of care.

Additional procedures will involve the following:

- 1) Following consent, but prior to the operation we will complete routine in-office fiberoptic laryngoscopy to assess baseline vocal cord function
- 2) Prior to intubation, the patient will receive glycopyrrolate 0.004 mg/kg, as per typical pre-anesthetic dosing regimen, to decrease airway and mucous membrane secretions
- 3) Upon intubation, the video laryngoscope will be passed under direct vision and secured alongside the endotracheal tube. Vocal cords will be positioned in the visual field of the laryngoscope before beginning the operation
- 4) Following video laryngoscopy, and initiation of the procedure, the ipsilateral vagus nerve will be tested using nerve stimulation (per standard protocol) to ensure good distal nerve conduction and identify potential non-recurrent laryngeal nerve anatomy
- 5) At all points during the procedure where intraoperative nerve monitoring is used, information about vocal cord motion from video laryngoscopy will also be recorded. Specifically, we will record the neuropraxia index from the nerve monitor, and whether vocal cord function is concordant with the neuropraxia index
- 6) At the conclusion of resection, the recurrent and superior laryngeal nerves will be assessed with IONM, the vagus will be assessed with IONM, and lastly the vocal cords will be assessed with IOVL. This sequence is consistent with the describe protocol for IONM for testing the vagus and recurrent nerve prior to resection, and then again in reverse order following resection (V1R1R2V2).
- 7) After conclusion of the procedure and final surgical closing, prior to extubation, vocal cord function will again be assessed with video laryngoscopy
- 8) At standard 1-week and 3-month post-operative follow-up we will also perform routine fiberoptic laryngoscopy, per common practice, to assess vocal cord function. Patients will be asked to complete a brief questionnaire at both of these visits

Medical records will be used to collect the vast majority of data required for this study. In addition, patients will be asked to complete a brief questionnaire at both the standard 1-week and 3-month follow up visits.

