6.3 MEASURES TO MINIMIZE BIAS: RANDOMIZATION AND BLINDING

N/A

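### The surgeon's reading of the nerve monitor alone is not recorded before the video laryngoscopy result is available, so which readings count as ambiguous can be influenced by that result

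*Protocol*

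**What the plan says.** The Study Description in section 1.1 sets the aim as "how frequently the use of IOVL provided confirmatory or additional information that may affect surgeon decision-making when IOLNM alone is ambiguous", or when the equipment malfunctions or fails. Section 2.1 repeats both situations.

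Ambiguity is described in two ways. Sections 1.1 and 4.3 say of the monitor's audio cues and the visible muscle movement: "This information can be ambiguous and subject to judgement of the surgeon". Section 2.2 adds: "Often the actual NPI is very close to 100, either higher or lower, and interpretation of nerve integrity in this range is ambiguous". It gives no limits for that range.

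On conduct, section 4.1 step 3 states: "Vocal cords will be positioned in the visual field of the laryngoscope before beginning the operation". Step 5 has IOVL information recorded at every point where the monitor is used, and continues: "Specifically, we will record the neuropraxia index from the nerve monitor, and whether vocal cord function is concordant with the neuropraxia index". Section 6.1.2 repeats these steps. Step 6 places IOVL after the nerve and vagus tests at the end of resection. Section 4.1 closes with: "Medical records will be used to collect the vast majority of data required for this study".

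The section headed "6.3 MEASURES TO MINIMIZE BIAS: RANDOMIZATION AND BLINDING" contains only N/A. Section 2.2 expects that surgeons may act on what IOVL shows when the monitor is ambiguous.

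**The concern.** To say how often a second test helps when the first is ambiguous, the verdict on the first test has to be reached without the second. Here that verdict is a judgement, and it is not listed among the items recorded at each monitoring point. Nor does any step place it before IOVL. It can therefore be formed, or reconstructed later, with the IOVL result known.

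A borderline reading may be more readily remembered as ambiguous when IOVL gave a useful answer. Equally, a reading that was doubtful at the time may be remembered as fine once IOVL showed normal movement, and so drop out of the count. Either way, membership of the ambiguous group depends partly on the test being evaluated.

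The result is meant to inform whether routine laryngoscopy is needed (section 2.3.2) and whether larger studies are warranted (section 5.5). An analysis plan cannot repair this later, because a judgement that was never recorded cannot be recovered.

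**Working it through.** **Passages side by side**

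1. What is counted: IOVL help among readings that are ambiguous on the monitor alone (1.1, 2.1).
2. Who decides ambiguity: the surgeon (1.1, 4.3). There is no numerical rule; section 2.2 has a neighbourhood of 100 without a band.
3. When the IOVL picture is available: from before the operation begins (4.1 step 3).
4. What is specified at each monitoring point: the index and a concordance entry (4.1 step 5, 6.1.2). Concordance needs both results in hand, so it is not a reading of the monitor alone.
5. What protects the order: nothing during the procedure (6.3 is N/A). Step 6 sets a testing order at the end of resection only and does not have an interpretation entered before IOVL is viewed.

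Items 2 to 5 together leave the ambiguity label open to the IOVL result.

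**The plan's own figure**

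The protocol gives no expected number of ambiguous cases. Its only count for a target situation is 8-15 malfunction cases, from 75-125 patients at 10-15% (5.5). The lower end reproduces: 75 × 0.10 = 7.5. The upper end does not: 125 × 0.15 = 18.75, and 15 corresponds to 100 × 0.15. Nothing below depends on this count.

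**Illustration on assumed values**

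From the documents: N = 125 (Synopsis). Assumed: one reading per patient; a share b of readings is borderline; IOVL is informative in a share h of those. A borderline reading is labelled ambiguous with probability q1 if IOVL was informative and q0 if it was not.

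- Labelled ambiguous = N·b·[h·q1 + (1−h)·q0]
- Helped = N·b·h·q1
- Apparent helped share = h·q1 / [h·q1 + (1−h)·q0]

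With b = 0.20 there are 125 × 0.20 = 25 borderline readings.

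| h | q1 / q0 | Helped | Labelled ambiguous | Apparent share |
|---|---|---|---|---|
| 0.5 | 0.5 / 0.5 | 12.5×0.5 = 6.25 | 6.25+6.25 = 12.5 | 50% |
| 0.5 | 0.7 / 0.3 | 12.5×0.7 = 8.75 | 8.75+3.75 = 12.5 | 70% |
| 0.5 | 0.9 / 0.1 | 12.5×0.9 = 11.25 | 11.25+1.25 = 12.5 | 90% |
| 0.5 | 0.3 / 0.7 | 12.5×0.3 = 3.75 | 3.75+8.75 = 12.5 | 30% |
| 0.7 | 0.5 / 0.5 | 17.5×0.5 = 8.75 | 8.75+3.75 = 12.5 | 70% |
| 0.7 | 0.7 / 0.3 | 17.5×0.7 = 12.25 | 12.25+2.25 = 14.5 | 84.5% |
| 0.7 | 0.9 / 0.1 | 17.5×0.9 = 15.75 | 15.75+0.75 = 16.5 | 95.5% |

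Where q1 = q0 the share equals h, as it should. Otherwise it departs from h although the underlying readings are the same. The share does not contain b or N, so varying b over 10-30% rescales the counts only. The fourth row shows that the bias can also run downwards.

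**The case against.** Several points on the other side stand.

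- **The monitor is recorded on its own.** The index is a displayed device value and IOVL cannot change it. (Section 2.2 calls it the nerve power index and section 4.1 the neuropraxia index; I take them to be the same value.) A reader might infer that IOLNM alone is never measured. That goes too far: the index is captured, and what is missing is the interpretation that also draws on tone and muscle movement. A band around 100 fixed in advance would give part of the protection, but none is stated.
- **Discordance.** A reader might infer that calling a reading ambiguous removes it from the discordant cases. The text does not support this. Concordance is judged against the index, and nothing makes ambiguous and discordant mutually exclusive.
- **Primary measure.** The Synopsis endpoint and section 3 count how often IOVL adds data to IOLNM, without restriction to ambiguous readings. Ambiguity defines a situation of specific interest, not the denominator of the whole primary measure.
- **Malfunction.** Equipment failure is largely a matter of fact and much less exposed.
- **What the surgeon sees.** The protocol does not say who watches the IOVL picture. That the surgeon has it in view when judging the monitor is an inference from the scope's position, the N/A in section 6.3 and the expectation that surgeons may act on IOVL.
- **Source of data.** The reliance on medical records need not cover these readings: step 5 describes recording during the procedure, and section 10.1.9.1 provides worksheets whose fields are not shown.

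That the study is a descriptive pilot limits the consequences but does not remove the point, since the description sought includes this frequency.

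**Conclusion.** The point holds in a limited form. As written, the protocol does not list the surgeon's interpretation of the monitor alone among the entries it specifies, and does not fix it before the IOVL result is available. The ambiguous group can therefore be shaped by IOVL, and the frequency of help within that group may be biased.

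Neither size nor direction can be computed from the documents, which give no rate of ambiguous readings and nothing on how labels would shift. The spread of 30% to 90% around a true 50% rests wholly on the assumed values in the working and on one reading per patient, whereas the protocol takes several.

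A reader might infer that the study's findings as a whole are compromised. They are not: the index, the concordance entry and the malfunction cases largely escape. This is an inexpensive improvement to one component of a pilot.

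**What to change.** In section 4.1 step 5 and section 6.1.2, add one worksheet field at each monitoring point for the surgeon's interpretation of the monitor alone: intact, ambiguous, lost, or no usable reading. State that it is given and entered before the surgeon looks at, or is told, the IOVL result, and that it is not altered afterwards. Then enter the IOVL finding.

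The laryngoscope keeps running throughout. Turning the picture away from everyone would lose the movement evoked by that stimulation. The IOVL finding can come from a team member watching the scope, from recorded video, or from the next routine stimulation. The protocol names no observer, so it should say which applies. The first two keep both entries on the same stimulation.

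Use only the first entry to define the ambiguous cases, report the raw index beside it, and replace the N/A in section 6.3 with a sentence describing this order.

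The cost is one extra entry per reading and a delay of seconds before the surgeon consults IOVL. If no one but the surgeon watches the scope, one of the other two sources has to be arranged. No clinical decision rule changes.

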1.2 SCHEMA

Flow Diagram

1.3 SCHEDULE OF ACTIVITIES

	Pre-screening (Pre-consent)	Visit 1 Day 1	Visit 2 Day of surgery	Visit 3 1 week follow- up	Visit 4 3 month follow- up
Screen Clinic Schedule and Review Eligibility	X				
Informed Consent		X			
Routine fiberoptic laryngoscopy		X			
Video laryngoscope used during standard of care operation			X		
Routine fiberoptic laryngoscopy				X	
Routine fiberoptic laryngoscopy					X

2 INTRODUCTION

2.1 STUDY RATIONALE

We seek to assess the degree to which intraoperative video laryngoscopy used in conjunction with routine intraoperative nerve monitoring provides additional data on nerve integrity and vocal cord function for patients undergoing neck procedures that place the recurrence and superior laryngeal nerves at risk for injury or postoperative dysfunction. We want to see how frequently the information gained from video laryngoscopy may provide data on the vocal cord function in situations of ambiguous data from the nerve monitor, or in cases of equipment malfunction or failure of the nerve monitor. We would also like to assess the frequency of discordance in evaluation of intraoperative nerve monitoring, which is an indirect measure of vocal cord function via nerve integrity, with direct evaluation of vocal cord function via video laryngoscopy.

2.2 BACKGROUND

Thyroid and re-operative parathyroid surgery are technically demanding surgeries involving highly intricate anatomy. The recurrent laryngeal nerve (RLN) is the most important structure at risk during these procedures. The gold standard for protecting the nerve is identifying it through careful dissection before proceeding with the removal of the thyroid gland. The variability in the nerve's course can lead to trouble with identification and increase the risk of injury when surgeons are inexperienced. Although the rate of injury to the nerve has been reported to be relatively low—up to 6% for temporary paresis and up to 2% for paralysis—the consequences of injury can be devastating and thus lowering the injury rate even more is desirable. Data on the use of IOLNM was first published in 2001, and IOLNM has become a widely used adjunct for identifying the RLN and allowing real-time identification and functional assessment of the RLN in the operative field. It also provides information on the status of the superior laryngeal nerve status and function.

IOLNM is an indirect measure of vocal cord function. It provides information on nerve integrity via electromyography (EMG). The feedback the surgeon receives from the system is based on the amount of current necessary to stimulate vocal cord movement, with higher currents indicating worse signal transduction through the nerve, and a loss of signal indicating a severely injured or divided nerve. Surgeons are extrapolating vocal cord function based on auditory cues which indicate nerve integrity, as well as graphical information of the amplitude of the signal (known as the NPI or nerve power index), but do not routinely visualize vocal cord function in real time when making decisions during the procedure. In our experience, the current system has some limitations. The nerve power index (NPI) is a value displayed by the IOLNM system as an expression of nerve function, with higher numbers indicating better nerve conduction. The quality of conduction is audibly expressed by a two-tone system, with a higher-pitched tone occurring with an NPI >100, and a lower-pitched tone occurring with an NPI <100. Often the actual NPI is very close to 100, either higher or lower, and interpretation of nerve integrity in this range is ambiguous. Direct interpretation of vocal cord function could be of greater use to the surgeon at these times. We have also experienced system failures, either due to a break in the small wires of the electrode leads, or computer hardware or software malfunction, any of which can lead to the inability to use the IOLNM. In our experience, some form of failure or malfunction of the IOLNM system occurs in 10-15% of operative cases.

>100, and a lower-pitched tone occurring with an NPI <100. Often the actual NPI is very close to 100, either higher or lower, and interpretation of nerve integrity in this range is ambiguous. Direct interpretation of vocal cord function could be of greater use to the surgeon at these times. We have also experienced system failures, either due to a break in the small wires of the electrode leads, or computer hardware or software malfunction, any of which can lead to the inability to use the IOLNM. In our experience, some form of failure or malfunction of the IOLNM system occurs in 10-15% of operative cases.

Visualization of vocal cord function through an independent system offers another means to assess recurrent laryngeal nerve integrity in these situations.

Patients who are undergoing bilateral procedures may benefit from the addition of video laryngoscopy. At times, the decision to proceed with the second half of a procedure is made based on the perceived integrity of the recurrent laryngeal nerve. There are times when the intraoperative nerve monitor provided ambiguous data about nerve integrity, or has equipment malfunction or failure and no data are available. Video laryngoscopy may give direct information about vocal cord function, and confirmation of vocal cord function in the setting of ambiguous data from the nerve monitor may prompt surgeons to proceed with surgery, or terminate without performing contralateral procedures, based on demonstrated vocal cord function.

This represents a pilot study to first describe the use of IOVL in conjunction with IOLNM during thyroid and reoperative parathyroid procedures.

